## Early Withdrawal From the Study

If a subject is lost to follow-up, or is unwilling to have a remote assessment performed, the subject will be considered an early withdrawal. Sites will be reminded to follow the procedures outlined in the protocol.

## **Protocol Deviations**

All COVID-19 related protocol deviations will be reported and will be summarized in the Clinical Study Report.

1. INTRODUCTION

This Statistical Analysis Plan (SAP) describes the W96 analysis that will be performed after the last subject enrolled in the open-label extension phase completes the Week 96 visit, or prematurely discontinues from the study. The final analysis will be described in a separate SAP.

1.1. Trial Objectives

The primary objective of this study was to demonstrate noninferiority in efficacy of a D/C/F/TAF once-daily single-tablet regimen relative to continuing the current bPI combined with FTC/TDF in virologically-suppressed (HIV-1 RNA <50 copies/mL) HIV-1 infected subjects, in regard to the proportion of virologic rebounders (defined as having confirmed HIV-1 RNA \geq 50 copies/mL through Week 48, or in case of early discontinuation a last single viral load of HIV-1 RNA \geq 50 copies/mL) with a maximum allowable difference of 4%.

The secondary objectives of this study were:

- To evaluate superiority of switching to a D/C/F/TAF once-daily single-tablet regimen versus continuing the current bPI combined with FTC/TDF in regard to the proportion of virologic rebounders through Week 48, in case noninferiority is established;
- To evaluate the proportion of rebounders through Week 48 in the 2 treatment arms;
- To evaluate efficacy as determined by continued suppression of HIV-1 RNA (<20, <50, and <200 HIV-1 RNA copies/mL as defined by the FDA Snapshot analysis and time to loss of virologic response [TLOVR] algorithm) at Weeks 24 and 48 in the 2 treatment arms;
- To evaluate the safety and tolerability of the D/C/F/TAF regimen through 24 and 48 weeks of treatment;
- To evaluate the change from baseline in serum creatinine, eGFR for creatinine clearance (eGFR_{cr}, by Cockcroft-Gault and by Chronic Kidney Disease Epidemiology Collaboration [CKD-EPI]) and eGFR for cystatin C clearance (eGFR_{cyst}, by CKD-EPI) in the 2 treatment arms at Weeks 24 and 48;
- To evaluate the change from baseline in renal biomarkers at Weeks 24 and 48;
- To evaluate immunologic changes (CD4+ cell count) through 24 and 48 weeks of treatment in the 2 treatment arms;
- To evaluate adherence through drug intake (as derived by drug accountability data), and explore correlation with primary efficacy outcome;
- To evaluate resistance in subjects who show virologic rebound through Weeks 24 and 48 in the 2 treatment arms;
- To evaluate the steady-state pharmacokinetics of DRV in the D/C/F/TAF arm.

Secondary objectives in a bone investigation substudy performed at selected study sites:

- To evaluate the changes from baseline in bone biomarker levels at Weeks 24 and 48;

- To evaluate the safety of the 2 treatment arms as determined by the percent change from baseline in spine and hip bone mineral density (BMD) and changes in associated T-score at Weeks 24 and 48.

The secondary objectives to be assessed in the study extension:

- To evaluate long-term safety, resistance, and efficacy of the D/C/F/TAF regimen (until Week 96 and beyond).

1.2. Trial Design

This is a randomized, active-controlled, open-label, multicenter, Phase 3 study to evaluate the efficacy, safety and tolerability of switching to a D/C/F/TAF once-daily single-tablet regimen compared to continuing the current regimen consisting of a bPI (limited to DRV once daily with rtv or COBI, ATV with rtv or COBI, or LPV with rtv) combined with FTC and TDF (FDC; hereafter referred to as FTC/TDF) in virologically-suppressed (HIV-1 RNA <50 copies/mL), HIV-1 infected adult subjects over a 48-week treatment period.

The aim was to include approximately 1100 subjects in this study. Eligible subjects were to be currently treated with a stable ARV regimen consisting of a bPI (limited to DRV once daily with rtv or COBI, ATV with rtv or COBI, or LPV with rtv) combined with FTC/TDF only, for at least 6 consecutive months preceding the screening visit, and virologically suppressed with at least 1 plasma HIV-1 RNA measurement <50 copies/mL (or HIV-1 RNA undetectable by a local HIV-1 RNA test) occurring between 12 and 2 months prior to screening while being on the stable ARV regimen and have HIV-1 RNA <50 copies/mL at the screening visit. A single viral load elevation of ≥ 50 copies/mL and <200 HIV-1 RNA copies/mL after previously reaching viral suppression ('blip') within 12 months prior to screening is allowed, provided a subsequent viral load measurement is <50 HIV-1 RNA copies/mL (or HIV-1 RNA undetectable by a local HIV-1 RNA test) prior to screening. A change in pharmacokinetic booster (i.e., rtv or COBI) was allowed provided such a switch occurred no less than 1 month prior to the screening visit. Subjects treated with the combination DRV + COBI + FTC/TDF and having completed the required visits in the Gilead Sciences Inc. (GSI)-sponsored study GS-US-216-0130, and who fulfilled the present protocol criteria, were also given the option to participate in this study.

Prior to or at the baseline visit (Day 1), subjects who met all eligibility criteria were to be randomized in a 2:1 ratio to one of the following 2 treatment arms:

- D/C/F/TAF Arm: Switch to regimen of a single FDC tablet containing DRV 800 mg/ COBI 150 mg/ FTC 200 mg/ TAF 10 mg (D/C/F/TAF tablet) once daily, (n = 734);
- Control Arm: Continue current regimen consisting of a bPI (limited to DRV once daily with rtv or COBI, ATV with rtv or COBI, or LPV with rtv) combined with FTC/TDF only, (n = 367).

Randomization was stratified by the bPI used at screening.

Subjects from the D/C/F/TAF arm entered in the extension phase once they had completed their Week 48 visit. In addition, subjects in the control arm received the D/C/F/TAF tablet in the extension phase if, according to the investigator, they benefitted from it and if all conditions were fulfilled (which included adequate viral load results). Subjects from the control arm were required to attend a switch visit at Week

52 to receive D/C/F/TAF. All subjects in the extension phase had to attend visits every 12 weeks up to Week 96. As from Week 96, all subjects are offered the possibility to continue D/C/F/TAF treatment, if they wish and if they continue to benefit from it, until D/C/F/TAF becomes commercially available and is reimbursed, or can be accessed through another source in the country where he/she is living, or until the sponsor terminates clinical development. After Week 96, subjects should attend visits every 6 months.

Subjects who prematurely discontinued or changed study treatment during the treatment phase (from Day 1 to Week 48) or during the extension phase (only between Week 48 and 96) were required to complete the early study treatment discontinuation (ESTD) visit assessments within 72 hours of stopping/changing study treatment.

In addition, a 30-day follow-up (FU) visit was required for any subject who had an ongoing AE or serious adverse event (SAE) at the time of his/her last study visit (unless consent is withdrawn).

The study had a screening period of approximately 30 days starting from the signature of the informed consent form (ICF), a controlled treatment period of 48 weeks, an extension phase up to Week 96 and will have an optional extension beyond Week 96. A 30-day FU visit may take place as described above. A diagram of the study design is provided in [Figure 1](#).

Figure 1: Schematic Overview of the Study

	Baseline (Day 1)	Week 24	Week 48 Primary analysis	Week 96 or beyond
	Screening	Treatment phase		Extension phase
≤30 days prior to baseline	Treatment arm 1 (Test): D/C/F/TAF once daily (n=734)		D/C/F/TAF	ESTD and/or 30-day FU visit
	Treatment arm 2 (Control): Continue current bPI combined with FTC/TDF only (n=367)			

A planned Week 24 interim analysis was performed after the last subject completed 24 weeks on study, or prematurely discontinued from the study. The analysis was done mainly to evaluate the safety and tolerability of D/C/F/TAF. However, efficacy of the 2 treatment arms was also assessed and the results were shared with the DMC. The primary Week 48 analysis was performed after the last subject enrolled in the D/C/F/TAF arm reached Week 48 or the last subject enrolled in the control arm completed the Week 52 visit (whichever comes last), or prematurely discontinued from the study. The Week 96 analysis will be performed after the last subject completes 96 weeks on study, or prematurely discontinues from the study. The final analysis will be performed after all subjects have completed the extension phase (and the 30-day FU visit, if applicable).

The efficacy, as well as safety and tolerability, of the enrolled subjects and treatment regimens were monitored by an external DMC until Week 24 analysis.

1.3. Statistical Hypotheses for Trial Objectives

No formal statistical hypothesis is to be tested in the Week 96 analysis.

1.4. Sample Size Justification

A sample size of 1100 subjects yields 89% power. It was assumed that both treatment arms have a rebound rate of 4% (confirmed HIV-1 RNA ≥ 50 copies/mL up to, and including the upper bound of the Week 48 window or have discontinued prematurely, irrespective of reason, having the last available HIV-1 RNA ≥ 50 copies/mL), that the noninferiority margin is 4%, and that the significance level of the test is at a 1-sided, 0.025 level.

For the bone investigation substudy, with 300 subjects (200 in the D/C/F/TAF treatment arm versus 100 in the control arm) and assuming an inter-subject variability of 4%, there is approximately 98% power to detect a 2% difference between the D/C/F/TAF treatment arm and the control arm in percent change from baseline in BMD at the lumbar spine. Other power calculations are presented below.

BMD at the Lumbar Spine, Power Calculations

	Mean % Change from Baseline	Common Standard Deviation (%)	Power
N=300	2	3.5	>99%
		4	98%
	3	3.5	>99%
		4	>99%

1.5. Randomization and Blinding

Randomization

Central randomization was implemented in this study. Subjects were randomized in a 2:1 ratio to the investigational treatment arm (switch to D/C/F/TAF tablet), or the active control arm (maintain current regimen consisting of a bPI combined with FTC/TDF only). Randomization was stratified by the bPI used at screening (DRV with rtv or COBI, ATV with rtv or COBI, LPV with rtv). Randomization was based on a computer-generated schedule, constructed via random permuted blocks to ensure balance across treatment arms in each stratum of the stratification factors, and prepared before the start of the study by or under the supervision of the sponsor.

Blinding

As this is an open-label study, blinding procedures are not applicable.

2. GENERAL ANALYSIS DEFINITIONS

2.4. Treatment Arms

Following notations for the treatment arms in extension will be used:

- **Initial switch to D/C/F/TAF:** subjects who received D/C/F/TAF treatment at baseline of the treatment phase (initial switchers)
- **Late switch to D/C/F/TAF:** subjects who continued on their bPI treatment for 52 weeks and who switched to D/C/F/TAF treatment in the extension (late switchers)

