2.6. Analysis Sets

2.6.1. Intent-to-Treat Analysis Set

The intent-to-treat (ITT) analysis set includes all the subjects who were randomized and received at least 1 dose of treatment subsequent to randomization in the study. Efficacy data up to the last dose date of the treatment are included. The safety analysis (including all data collected at the 30-day FU visit) is also performed on this analysis set.

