5. SAFETY

For initial switchers, comparative treatment phase (study baseline to Week 48), extended treatment phase (Week 48 to Week 96) as well as combination of both phases (study baseline to Week 96) will be presented in the tables. For late switchers, comparative treatment phase (study baseline up to the switch) and extended treatment phase (from the switch to Week 96) will be presented.

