5.4.2. Analysis Methods

A summary will be provided for the following treatment-emergent adverse events:

- any adverse events,
- serious adverse events,
- deaths due to AE,
- adverse events by toxicity grade (as well as AEs with toxicity grade at least 2 and AEs with toxicity grades 3 or 4),
- AEs at least possibly related to study medication,
- AEs for which the medication was temporarily/permanently stopped,
- serious adverse events that were at least possibly related to the medication.

Incidences of AEs for above mentioned analyses will also be presented by SOC and preferred term. There will be no formal statistical testing.

Summary of events and incidence tabulations for individual adverse events will be provided for AEOI and also for ADRs.

AIDS defining illness based on WHO clinical staging will be tabulated.

The number and percentage of subjects who experienced fracture events (subgroups Fracture, possibly osteoporotic and Fracture other of the Bone AEOI for fractures) will be summarized by treatment group.

Selected safety endpoints will be explored by subgroups defined in section 2.7.2. Details for subgroup analyses of safety endpoints will be provided in the DPS.

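### SAP 2.4 and 5 disagree with SAP 2.6.1 on which control subjects belong in the comparative-phase safety displays of the Week 96 analysis

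*SAP*

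**What the plan says.** SAP 2.4 opens with "Following notations for the treatment arms in extension will be used" and gives two labels. *Initial switch* covers "subjects who received D/C/F/TAF treatment at baseline of the treatment phase (initial switchers", with no requirement to complete any period. *Late switch* covers "subjects who continued on their bPI treatment for 52 weeks and who switched to D/C/F/TAF treatment in the extension (late switchers". The switch was not automatic: under SAP 1.2, control subjects received D/C/F/TAF "if, according to the investigator, they benefitted from it and if all conditions were fulfilled (which included adequate viral load results".

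SAP 5 presents the comparative phase for both groups. For the control side the wording is "For late switchers, comparative treatment phase (study baseline up to the switch". The same two-group scheme recurs elsewhere:

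- SAP 2.9 defines reference values only for these two groups.
- SAP 3.6 plans baseline-to-switch adherence only for the *Late switch* arm.
- SAP 5.6.2 shows comparative-phase weight for these two groups.

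SAP 2.6.1 points the other way. The ITT set "includes all the subjects who were randomized and received at least 1 dose of treatment subsequent to randomization in the study", and the safety analysis is to be run on that set. Among the summaries in SAP 5.4.2 are deaths due to adverse events and "AEs for which the medication was temporarily/permanently stopped".

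**The concern.** Under 2.4 a control subject belongs to *Late switch* only if two things happened after randomisation: staying on the bPI for 52 weeks, and then switching. If that group is also the control column for the period before the switch, membership depends on what happened during the very period being tabulated. The *Initial switch* column has no such condition. A table of deaths, serious adverse events or treatment stops would then set everyone who started D/C/F/TAF beside only those control subjects who got through the period and went on to switch.

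This matters because protocol 11.1.2 lists serious adverse events and premature discontinuations due to adverse events, through 24, 48 and 96 weeks, as a secondary endpoint. A reader of the Week 96 report would naturally read the two comparative-phase columns against each other.

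**Working it through.** The plan gives no figure on this point to reproduce. The check is to place each kind of subject under the stated rules, then illustrate the size.

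**Step 1. Where each subject goes**

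| Subject | Column under 2.4 with 5 | In the 2.6.1 set? | Comparative-phase end date in 2.5.1 |
|---|---|---|---|
| Control, 52 weeks on bPI, then switched | *Late switch* | Yes | Day before first D/C/F/TAF |
| Control, died or permanently stopped before the switch | None | Yes | Withdrawal rule |
| Control, completed but did not switch | None | Yes | None, unless coded as withdrawn |
| D/C/F/TAF arm, died or stopped early | *Initial switch* | Yes | Withdrawal rule |

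Rows two and three carry the conflict: these subjects are in the analysis set and have no column.

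**Step 2. Which entries are affected on the literal reading.** Deaths before the switch and permanent bPI stops before the switch cannot occur in *Late switch*. Temporary interruptions and all other adverse events in switchers still appear. The line on stopped medication need not be empty either: an event that began before the switch and led to stopping D/C/F/TAF afterwards might be counted in the comparative phase, and the SAP does not state the allocation rule.

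**Step 3. Size, for illustration.** The planned arms are 734 and 367 (SAP 1.2). The documents give no non-switch rate and no event rates, so every percentage below is an assumption.

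- Subjects leaving the column: 367 × 0.05 = 18.4, about 18 (349 left); 367 × 0.10 = 36.7, about 37 (330 left).
- Permanent stops for adverse events, true rate 2% in both arms: 734 × 0.02 = 14.7, about 15 in *Initial switch*; 367 × 0.02 = 7.3, about 7 in the full control arm. Where these are bPI stops before the switch, *Late switch* shows none of the 7.
- Serious adverse events, 4% in the 330 who switch and 20% in the 37 who do not: (330 × 0.04 + 37 × 0.20) / 367 = 20.6 / 367 = 5.6% for the full arm, against 4.0% in *Late switch*. With 40% in the 37: (13.2 + 14.8) / 367 = 7.6%, again against 4.0%.

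**Step 4. Direction.** For pre-switch deaths and permanent bPI stops, the omission can only lower the control count. For other events a second feature works the opposite way. The late switchers' comparative phase runs to the day before first D/C/F/TAF, around Week 52, while that of initial switchers ends at Week 48. That is (52 − 48) / 48 = 8.3% more observation time, which raises crude control incidence. The documents do not show which effect is larger.

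**The case against.** The strongest reply is that 2.4 only supplies labels for the extension, and that the population rule is 2.6.1. Other sections fit that view. SAP 2.5.1 builds phases for every subject and gives the comparative phase a withdrawal end date that is not tied to one arm. SAP 3.5 tabulates discontinuations before Week 96, with reasons, per arm, and adds a Kaplan-Meier graph of time to discontinuation. Control discontinuations are therefore not planned to vanish from the report. Nor is there a formal between-arm safety test here: the SAP covers Week 96 only, SAP 1.3 and 4.4.1 make it descriptive, and SAP 5.4.2 rules out formal testing of adverse events. The Week 48 comparison had already been performed (SAP 1.2).

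Much of this stands. A reader might infer that the control columns contain only survivors by construction. The documents do not support that, because 2.6.1 is an equally explicit competing instruction. A reader might also infer that the randomised Week 48 safety comparison is compromised. Nothing shows that; its SAP is not among the documents.

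What the reply does not do is settle the matter. SAP 2.6.1 says who is eligible for analysis, not which column holds them. The withdrawal rule supplies a date, not a group. The disposition table does not place the adverse events, deaths or laboratory grades of control non-switchers in any safety table. The Data Presentation Specifications may fix the column headers, but that document cannot be seen here.

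**Conclusion.** The SAP conflicts with itself on the denominator of the control comparative-phase safety displays. On the literal reading of 2.4 with 5, control subjects who died, permanently stopped their bPI before the switch, or completed without switching have no column, and pre-switch deaths and permanent bPI stops cannot appear for control. On 2.6.1 they should be included.

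The reach is limited to the descriptive Week 96 re-presentation of the comparative phase. Its size cannot be determined: the 18 to 37 subjects rest on an assumed 5% to 10% non-switch rate applied to the planned 367, and the event-rate examples are assumptions throughout. It would also go too far to conclude that D/C/F/TAF must look worse overall. That direction holds only for pre-switch deaths and permanent bPI stops on the literal reading; for other adverse events the net direction is open. The conflict is still worth resolving, because one reading selects the control column on a post-randomisation outcome.

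**What to change.** - In SAP 2.4, add a group for the control arm (bPI + FTC/TDF) made up of all randomised and treated control subjects. Use it as the control column for all comparative-phase safety outputs in SAP 5 and for time points before the switch.
- Keep *Late switch* for extended-phase outputs only.
- In SAP 2.5.1, add a comparative-phase end date for control subjects who complete but do not switch. In SAP 2.9, state that study baseline is the reference for the new group.
- Print the N of each group in the column headers.

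The cost is SAP wording and one extra grouping variable, with no new data. The one drawback is that control Ns will differ between comparative-phase and extended-phase columns, which the printed Ns make plain. If the sponsor already intends the full control arm, a sentence in 2.4 and 5 saying so would settle the denominator; the missing end date would still need adding.

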2.5. Visit Windows

2.5.1. Trial Phases

Phases will be constructed for each subject as follows for adverse events, concomitant therapies, and for the determination of the worst-case/toxicity/change in the cross-tabulations.

Trial phase	Start date	End date
Screening	Minimum of Date of signing the informed consent and Date of the screening visit	1 day before start of treatment
Comparative Treatment Phase	Date of the first intake (after randomization)	
For initial D/C/F/TAF subjects, in order of priority:
 
 - Week 48 visit date; if missing then - Projected Week 48 visit date, where projected Week 48 visit date = baseline visit date + (7 *48) 
For late switchers: Date of first D/C/F/TAF intake-1 day
 
In case of withdrawal use:
 
 - Minimum(last intake date of study drug, study withdrawal date) + 2 days
Extended Treatment Phase (Extension)	Last Date of Comparative Treatment Phase +1 day	
 - Week 96 visit date; if missing then - Projected Week 96 visit date, where projected Week 96 visit date = baseline visit date + (7 *96) 
In case of withdrawal use:
 
 - Minimum (last intake date of study drug, study withdrawal date) + 2 days
Follow-up	End of last treatment phase +1 day	Trial termination date for all groups (date of last contact)

Data up to each subject's Week 96 visit are in scope for this analysis, DXA data (DP domain) up to Week 96 visit+28 days, and if applicable, any (confirmatory) viral load or genotype/phenotype results immediately subsequent to Week 96 (up to 6 weeks).

2.5.2. Analysis Time points

All visits/assessments will be allocated to the following time points as per the table below, based on the number of days in the study, calculated as “assessment date – start date of comparative treatment phase + 1 day” for Comparative Treatment/Extended treatment and Follow-up phase.

The following time intervals will be used for reporting of efficacy as well as safety data:

Phase	Visit	Target day	Analysis time point	Time interval (days)
Screening	1	-∞	Screening	< Day 0
Comparative Treatment Phase	2	1	Baseline ^a	≤Day 1
	3	15	Week 2	Day 2 – Day 21
	4	29	Week 4	Day 22 – Day 42
	5	57	Week 8	Day 43 – Day 70
	6	85	Week 12	Day 71 – Day 126
	7	169	Week 24	Day 127 – Day 210
	8	253	Week 36	Day 211 – Day 294
	9	337	Week 48 ^b	Day 295 – Day 378
Extended treatment phase (Extension)	10	421	Week 60 (Week 12)	Day 379 – Day 462
	11	505	Week 72 (Week 24)	Day 463 – Day 546
	12	589	Week 84 (Week 36)	Day 547 – Day 630
	13	673	Week 96 ^c (Week 48)	Day 631 – Day 714
Follow-up	14	31	Follow-up	Day 1 onwards

^a Only the record closest to target day 1 will be allocated to analysis time point ‘Baseline’, all records prior to day 1 are assigned to ‘Screening’.

For DXA scans a scan up to 28 days post-baseline was used as a baseline scan.

^b DXA scan up to 28 days post-Week 48 was used as the Week 48 scan

^c DXA scan up to 28 days post-Week 96 was used as the Week 96 scan.

Note, for Initial Switchers to D/C/F/TAF, period “Baseline-Week 96” will include visits from Comparative treatment phase and Extended treatment phase.

Unless specified otherwise, if two visits fall within the same interval, the one closest to the target day will be used for the analysis displays and graphics in order to have only one evaluation per subject per analysis time point. However, all data will be presented in the listings. If distances of both visits to the target day are equal, the visit latest in time will be used. If multiple visits that fall within the same analysis window have the same date/time, the one with the highest sequence number will be used.

